5.5. Justification for Dose

A galcanezumab 240-mg loading dose (2 consecutive injections of 120 mg each) or a dose of 140 mg erenumab (2 consecutive injections of 70 mg each) will be administered by subcutaneous injection because both galcanezumab and erenumab have been approved in the US at these respective doses for migraine prevention.

6.1. Inclusion Criteria

- [2] Have a diagnosis of migraine (1.1 and 1.2 ICHD), with or without aura, ~~or chronic migraine~~, as determined by the study investigator and in consideration of International Headache Society International Classification of Headache Disorders – 3rd edition guidelines (ICHD-3 2018).
- [3] Have a frequency of less than 15 monthly headache days of which up to 14 can be migraine headache days.

[43] Patients can be on no more than 1 other migraine preventive treatment (except for tricyclic antidepressants and verapamil) as long as:

- that patient has had a stable dose of the oral migraine preventive treatment for a minimum of 2 months

or

- patients ~~with chronic migraine~~ that have received onabotulinumtoxinA for a minimum of 2 cycles prior to Visit 1.

6.2. Exclusion Criteria

[210] Patients with a body mass index (BMI) of ≥ 50 –40 kg/m².

[276] Patients currently receiving a mAb CGRP antagonist ~~on CGRP antagonists~~ or have ~~taken~~ received a mAb CGRP antagonist within the past 6 months prior to Visit 1.

[28] Have received an oral CGRP antagonist (gepant) 14 days prior to Visit 1.

6.4. Screen Failures

- Exclusion criterion 27, 28, and 31: Patients using a concomitant medication that requires a stable dose for a specific duration prior to Visit 1 may be rescreened if additional time is needed to meet the duration requirement.

7.1. Treatments Administered

Table CGBC.7.1. Treatment Regimens

Regimen	Dose
	Day 7 ± 2
Galcanezumab 240 mg	240 mg (2 × 120-mg SC injection)
Erenumab 140 mg	140 mg (2 × 70 140-mg SC injection)

Abbreviation: SC = subcutaneous.

7.2. Packaging and Labeling

Galcanezumab and erenumab will be supplied as an injectable solution in 1-mL, single-dose, prefilled, disposable AI pen. Each AI pen of galcanezumab is designed to deliver 120 mg/mL, and each AI pen of erenumab is designed to deliver ~~140~~ 70 mg/mL. All AI pens will be supplied in single pen cartons, with the site to select the appropriate quantity of AI pens, specific to the planned treatment schedule. Two galcanezumab AI pens are needed for the galcanezumab (240 mg) treatment. ~~One~~ Two erenumab AI pens are needed for the erenumab (140 mg) treatment.

7.2. Method of Treatment Assignment

To achieve between-group comparability, the randomization will be stratified by site, ~~concurrent migraine preventive treatment~~ BMI category (Yes/No $<30 \text{ kg/m}^2$, $\geq 30 \text{ kg/m}^2$), and by baseline migraine frequency (<8 migraine headache days versus ≥ 8 migraine headache days) ~~migraine classification of episodic or chronic~~.

7.2.1. Selection and Timing of Doses

The study treatment will be administered only once at Visit 3 ~~after expulsion of the WMC has been confirmed~~.

7.3. Blinding

This is an ~~open-label~~ single-blind study. Only the investigator, site personnel, and sponsor will know the randomized treatment after randomization. Site Personnel are responsible to ensure patients remain blinded to treatment (i.e., patients must not see the AI pens before, during, or after the drug administration). See the Manual of Operations for further details regarding blinding.

9.1.1. Primary Assessment of GI Transit Time

The WMC (Medtronic 2017) measures whole gut and regional gut (stomach, small bowel, and colon) transit times through measurement of pH, pressure, and temperature throughout the GI tract. Once enrolled into study, the patient will be asked to eat a SmartBar ~~with 120 mL water~~, followed by ingesting the WMC with 120 mL of water ~~with 50 mL of water~~. The patient will then be instructed to fast for an additional 6 hours after the WMC is administered and wear an external data recorder for up to 5 days. The WMC is a 4.5-g indigestible single-use, 27×12 mm cylindrical capsule. Data are transferred to the accompanied wearable external data recorder and displayed and analyzed using MotiliGI™ version 3.1 software (Medtronic 2017).

9.2.1. Serious Adverse Events

Study site personnel must alert Lilly or its designee of any SAE within 24 hours of investigator awareness of the event via a sponsor-approved method. If alerts are issued via telephone, they are to be immediately followed by official notification on study-specific SAE forms. This 24-hour notification requirement refers to the initial SAE information and all follow-up SAE information. ~~Patients with a serious hepatic AE should have additional data collected using the eCRF.~~

9.2.1.1. Suspected Unexpected Serious Adverse Reactions

Suspected unexpected serious adverse reactions (SUSARs) are serious events that are not listed in the galcanezumab IB or the erenumab US package insert (USPI) and that the investigator identifies as related to study treatment or procedure. United States 21 CFR 312.32 and European Union Clinical Trial Directive 2001/20/EC and the associated detailed guidances or national regulatory requirements in participating countries require the reporting of SUSARs. Lilly has

procedures that will be followed for the identification, recording, and expedited reporting of SUSARs that are consistent with global regulations and the associated detailed guidances.

10.3.3.1. Primary Analyses

The primary analysis will be performed using an analysis of covariance (ANCOVA) model. The analysis will include the categorical effects of treatment and all randomization stratification factors (site, ~~concurrent use of migraine preventive treatment Yes vs No, and migraine classification of episodic or chronic~~ baseline migraine frequency, and BMI category; see Section 7.2), as well as the continuous baseline CTT. Least squares mean change from baseline in each treatment group will be tested to detect any change in CTT between pre- and post-drug administration.

### Galcanezumab-gnlm (LY2951742) Migraine

A multicenter, randomized, single-blind, Phase 4 study with 2 study periods in patients with migraine who are deemed eligible for preventive treatment by the study investigator. The study has 2 periods: a screening period to determine patient eligibility and lead-in with a baseline WMC test; and a single-blind treatment period with post-study treatment WMC test.

Eli Lilly and Company  
Indianapolis, Indiana USA 46285  
Protocol I5Q-MC-CGBC

Statistical Analysis Plan Version 1 electronically signed and approved by Lilly:  
12 March 2020  
Statistical Analysis Plan Version 2 electronically signed and approved by Lilly on date  
provided below.

Approval Date: 29-Sep-2020 GMT

### 3. Revision History

Statistical Analysis Plan Version 1 was approved prior to the first patient visit.

Statistical Analysis Plan Version 2 was approved prior to the first patient visit. The following updates were made to coincide with a protocol amendment:

- Section 5.1 and throughout, updated to single-blind study as the protocol was updated to a single-blind study design.
- Section 5.3 and throughout, updated stratification factors. Removed concurrent migraine preventive treatment (Yes/No) and migraine classification of episodic or chronic; and replaced with body mass index category ( $<30\text{kg/m}^2$ ,  $\geq 30\text{ kg/m}^2$ ), and by baseline migraine frequency ( $<8$  migraine headache days,  $\geq 8$  migraine headache days).
- Section 6.2, with the removal of chronic migraine patients, the derivation of chronic versus episodic has been removed.
- Section 6.3 was updated to include language about adjustments due to COVID-19.
- Section 6.8, substance use, medical history, and preexisting conditions were added to patient characteristics.
- Section 6.11, vital signs bullet was added, and a description of models used for safety analyses was provided.
- Section 6.11.2, treatment compliance was moved to this section.
- Section 6.11.6, analyses for vital sign data were added; previously no analyses were planned.
- Section 6.12, section on blinding was added since study design switched from open-label to single-blind.
- General formatting and grammatical edits were made throughout the document that did not change the meaning.

## 4. Study Objectives

### 4.1. Primary Objective

The primary objective is to evaluate colonic transit time (CTT) in patients with migraine 1 week prior to and 2 weeks after administration of an initial loading dose of galcanezumab 240 mg or erenumab 140 mg. The primary outcome measure is CTT in hours. The primary endpoint is the change from baseline in CTT after administration of galcanezumab or erenumab within each treatment group in hours at the end of Week 2.

### 4.2. Secondary and Tertiary Objectives

Table CGBC.4.1 shows the secondary and tertiary objectives and endpoints.

**Table CGBC.4.1. Secondary and Tertiary Objectives and Endpoints**

Objectives	Endpoints

Secondary Objectives
 
To evaluate transit time of the following segments of the gastrointestinal (GI) tract 1 week prior to and 2 weeks after administration of galcanezumab or erenumab:
 
 
• whole gut
 
• gastric emptying
 
• small intestine, and
 
• combined small and large bowel.
 
	
Change from baseline in GI transit time in each of the following segments after administration of galcanezumab or erenumab within each treatment group at the end of Week 2:
 
 
• whole gut transit time (WGTT), in hours
 
• gastric emptying time (GET), in hours
 
• small intestine bowel transit time (SBTT), in hours, and
 
• combined small and large bowel transit time (SLBTT), in hours.
 

To evaluate the frequency of contractions, motility index, and area under the pressure curve (AUC) by quartile in the colon to assess for correlation with colonic transit time (CTT) results.
	
Changes in pressure parameters from baseline:
 
 
• contraction freq/min
 
• motility index = <math>\ln(\# \text{ of contractions} \times \sum \text{pressure amplitudes} + 1)</math>, and
 
• Area under the pressure curve (AUC).
 

To evaluate number of weekly spontaneous bowel movements (un-aided by laxatives, enemas, or suppositories) prior to and after administration of galcanezumab or erenumab.
	
Change from baseline in number of weekly spontaneous bowel movements after administration of galcanezumab or erenumab within each treatment group at Weeks 2 and 4 post-treatment.

To evaluate GI symptom rating scale (GSRS) prior to and after administration of galcanezumab or erenumab.
	
Change from baseline in GSRS after administration of galcanezumab or erenumab within each treatment group at Weeks 2 and 4 post-treatment.

To evaluate the Bristol Stool Form Scale (BSFS) prior to and after administration of galcanezumab or erenumab.
	
Change from baseline in BSFS after administration of galcanezumab or erenumab within each treatment group at Weeks 2 and 4 post-treatment.

**Secondary and Tertiary Objectives and Endpoints**

[figure not shown]
Objectives	Endpoints

Tertiary/Exploratory Objectives
 
To evaluate the transit time between galcanezumab and erenumab for
 
 
• whole gut
 
• gastric emptying
 
• small bowel
 
• colon, and
 
• combined small and large bowel.
 
	
Change from baseline in transit time after administration of galcanezumab or erenumab between treatment groups at the end of Week 2 for
 
 
• WGTT, in hours
 
• GET, in hours
 
• SBTT, in hours
 
• CTT, in hours, and
 
• combined SLBTT, in hours.
 

To evaluate number of weekly spontaneous bowel movements (un-aided by laxatives, enemas, or suppositories) prior to and after administration of galcanezumab or erenumab.
	
Change from baseline in number of weekly spontaneous bowel movements after administration of galcanezumab or erenumab between each treatment group at Weeks 2 and 4 post-treatment.

To evaluate GSRS prior to and after administration of galcanezumab or erenumab.
	
Mean change difference from baseline in GSRS scores after administration of galcanezumab or erenumab between treatment groups at Weeks 2 and 4 post-treatment.

To evaluate the BSFS prior to and after administration of galcanezumab or erenumab.
	
Mean change difference from baseline in BSFS scores after administration of galcanezumab or erenumab between treatment groups at Weeks 2 and 4 post-treatment.

## 5. Study Design

### 5.1. Summary of Study Design

Study I5Q-MC-CGBC is a multicenter, randomized, single-blind, Phase 4 study with 2 study periods in patients with migraine who are deemed eligible for preventive treatment by the study investigator. The study has 2 periods: a screening period to determine patient eligibility and lead-in with a baseline wireless motility capsule (WMC) test and a single-blind treatment period with a post-study treatment WMC test.

Figure CGBC.5.1 illustrates the study design.

Abbreviations: LD = loading dose; SP = study period; WMC = wireless motility capsule.

Note: Single-Blind - only the investigator, site personnel, and sponsor will know the randomized treatment after randomization.

**Figure CGBC.5.1. Illustration of study design for Clinical Protocol I5Q-MC-CGBC.**

### 5.2. Determination of Sample Size

Assuming that the within-group mean difference in CTT is approximately 4.2 hours with a standard deviation of approximately 8, a sample of 30 patients in each treatment group will

provide 80% power to detect the difference within the treatment group. The total sample size for the study is 60 patients.

Assuming a 20% screen failure rate, approximately 75 patients may be screened to enroll 60 patients in the study. Eligible patients will be randomized in a 1:1 ratio to galcanezumab or erenumab to enroll approximately 30 patients in each treatment group.

### 5.3. Method of Assignment to Treatment

Patients who meet all criteria for enrollment will be randomized to single-blind treatment at Visit 3 in a 1:1 ratio to galcanezumab or erenumab. To achieve between-group comparability, the randomization will be stratified by site, body mass index (BMI) category ( $<30\text{kg/m}^2$ ,  $\geq 30\text{kg/m}^2$ ), and by baseline migraine frequency ( $<8$  migraine headache days,  $\geq 8$  migraine headache days). Assignment to treatment groups will be determined by a computer-generated random sequence using an interactive web-response system.

### 5.4. Measures

#### 5.4.1. Primary Measures

The SmartPill™ WMC technology (Medtronic, Minneapolis, MN, USA) will be used to evaluate total gastrointestinal (GI) transit time and segmental transit time. The WMC measures whole gut and regional gut (stomach, small bowel, and colon) transit times through measurement of pH, pressure, and temperature throughout the GI tract. Once enrolled in the study, patients will be asked to eat a SmartBar, followed by ingesting the WMC with 120 mL of water. Patients will be instructed to fast for an additional 6 hours after ingesting the WMC and to wear an external data recorder for up to 5 days. The WMC is a 4.5-g indigestible, single-use,  $27 \times 12$  mm cylindrical capsule. Data will be transferred to the wearable external data recorder and displayed and analyzed using Medtronic MotiliGI™ version 3.1 software (Medtronic, Minneapolis, MN, USA).

The baseline and postbaseline WMC tests will be assessed by expert readers who are blind to treatment assignment.

The primary outcome measure is CTT in hours. Secondary transit time outcome measures include the whole gut transit time in hours, gastric emptying time (GET) in hours, small intestine bowel transit time (SBTT) in hours, and small and large bowel transit time (SLBTT) in hours. All transit time outcome measures will be collected at baseline and 2 weeks after study drug administration.

Further secondary outcome measures include contraction, measured as frequency per minute, motility index, and AUC.

#### 5.4.2. Other Secondary Measures

**Gastrointestinal Symptom Rating Scale:** The Gastrointestinal Symptom Rating Scale (GSRS) is a validated 15-item questionnaire that evaluates the 5 common symptoms of GI disorders: abdominal pain, reflux, indigestion, constipation, and diarrhea. Items contain questions about

the past week using a 7-point categorical response scale ranging from no discomfort to very severe discomfort (Revicki et. al 1998; Khanna et al. 2017). Based on a factor analysis, the 15 GSRS items are summarized by the 5 scales, which are calculated by taking the mean of the items completed within an individual scale. The GSRS is grouped accordingly by

- abdominal pain – abdominal pain, hunger pains, and nausea
- reflux syndrome – heartburn and acid reflux
- diarrhea syndrome – diarrhea, loose stools, and urgent need to have a bowel movement
- indigestion syndrome – rumbling, bloating, belching, and increased flatus (breaking wind); and
- constipation syndrome – constipation, hard stools, and sensation of not completely emptying the bowels.

**Bristol Stool Form Scale:** The Bristol Stool Form Scale (BSFS) is 7-point ordinal scale of stool types ranging from the hardest (type 1) to the softest (type 7). Symptoms of constipation are related to harder stools (types 1 and 2), and symptoms of diarrhea are related to loose/liquid stools (types 6 and 7). Overall, stool types 3 to 5 are considered normal. The BSFS provides the patient with a pictorial representation of each type of stool (Blake et al. 2016).

**Spontaneous Bowel Movement Frequency Evaluation:** The spontaneous bowel movement (SBM) frequency evaluation is the number of spontaneous (nonintervention induced) bowel movements that a patient has had in the past 7 days. Patients are asked how many SBMs they have had in the past 7 days, and the information is collected on the case report form (CRF) for Visits 1, 3, 4, and 5.

## 6. A Priori Statistical Methods

### 6.1. General Considerations

General aspects of statistical analyses are described below.

Unless otherwise specified, analyses will be conducted for the intent-to-treat (ITT) population, which includes all patients who are randomized and receive at least 1 dose of study treatment. Patients in the ITT population will be analyzed according to the treatment group to which they are randomized. The ITT population will be the primary population for which statistical analysis are performed. When mean change from baseline is assessed, only patients with baseline and postbaseline measurements will be included in the analysis.

Investigative sites with fewer than 4 randomized patients per treatment group will be pooled for statistical analysis purposes.

All tests of within-group and between-group comparisons will be conducted at a 2-sided alpha level of 0.05, unless otherwise stated.

### 6.2. Adjustments for Covariates

The analysis of covariance (ANCOVA) model will include the categorical effects of treatment, pooled investigative site, BMI category ( $<30\text{kg/m}^2$ ,  $\geq 30\text{kg/m}^2$ ), and baseline migraine frequency ( $<8$  migraine headache days,  $\geq 8$  migraine headache days), as well as the continuous baseline value. Rules for pooling of investigative sites are described in Section 6.4.

For continuous measures with repeated postbaseline measurements, change from baseline will be analyzed using a restricted maximum likelihood (REML)–based mixed effects model for repeated measures (MMRM) technique. The analysis will include the fixed categorical effects of treatment, pooled investigative site, BMI category ( $<30\text{kg/m}^2$ ,  $\geq 30\text{kg/m}^2$ ), baseline migraine frequency ( $<8$  migraine headache days,  $\geq 8$  migraine headache days), week, and treatment-by-week interaction, as well as the continuous fixed covariates of baseline value and baseline-by-week interaction.

### 6.3. Handling of Dropouts or Missing Data

For the repeated measures analyses, the model parameters are simultaneously estimated using restricted likelihood estimation incorporating all of the observed data. Estimates have been shown to be unbiased when data are missing at random (MAR). Missingness due to COVID-19 does not depend on the outcome measurements and therefore will be considered MAR.

### 6.4. Multicenter Studies

Investigative sites with fewer than 4 randomized patients per treatment group will be pooled for analyses. If a pooled site has fewer than 4 randomized patients per treatment group, the site will be pooled with the next smallest site, determined to be the site with the smallest number of randomized patients, or if more than one site meets that criterion, the smallest site with the lowest investigator number. This process will continue until all pooled sites have 4 or more randomized patients per treatment group.

All analyses that are prespecified to include investigative site will use this pooled investigative site. The investigative site numbers will be included in the listings.

### 6.5. Multiple Comparisons/Multiplicity

All tests of within-group and between-group comparisons will be conducted at a 2-sided alpha level of 0.05, unless otherwise stated.

### 6.6. Analysis Populations

**Intent-to-treat (ITT) population:** All patients who are randomized and receive at least 1 dose of study treatment. Patients in the ITT population will be analyzed according to the treatment group to which they are randomized.

**Safety population:** All patients who are randomized and receive at least 1 dose of study treatment. Patients in the safety population will be analyzed according to the treatment they receive.

Other populations may be explored if appropriate, such as the ITT population excluding patients taking prohibited medications that are known to have an effect on GI motility or the WMC test.

### 6.7. Patient Disposition

The number and percentage of patients in the ITT population who complete the study or discontinue early will be summarized for both treatment groups. A detailed description of patient disposition will be provided at the end of the study.

Patient allocation by investigative site will be summarized for the ITT population. Patient allocation by investigative site will also be listed.

### 6.8. Patient Characteristics

The following patient characteristics at baseline will be summarized by treatment group for the ITT population:

- demographics (age, gender, ethnic origin, height, weight, and BMI)
- medical history and preexisting conditions
- total gut and segmental transit times
- GI symptom rating scale, SBM frequency, and BSFS, and
- alcohol, tobacco, caffeine, and nicotine consumption.

Medical history and preexisting conditions will be summarized by descending frequency of Preferred Term (PT) nested within System Organ Class (SOC). Medical history is defined as illness(es) that ended prior to the signing of informed consent. Preexisting conditions and adverse events (AEs) at baseline are those AEs occurring during the baseline/screening visits for the study period.

The percentage of patients who report a change in alcohol, tobacco, caffeine, or nicotine consumption during the study will be summarized.

## 6.9. Concomitant Therapy

The proportion of patients who received concomitant medication recorded on the general concomitant medication electronic case report form (eCRF) will be summarized for the ITT population. Treatment group comparisons, if needed, will be done using Fisher's exact test.

Concomitant therapies are defined those that were stopped during Study Period II or continued in Study Period II. If a medication was started and stopped on the same day as the first injection, it will be counted as a concomitant medication. If a medication was started before the first day of injection but was stopped on the same day of injection, it will not be counted as a concomitant medication.

## 6.10. Efficacy Analyses

### 6.10.1. Primary Outcome and Methodology

The primary analysis will evaluate the change from baseline in CTT (hours) after administration of an initial loading dose of galcanezumab 240 mg or erenumab 140 mg at the end of Week 2.

The primary analysis will be performed using an ANCOVA model including the categorical effects of treatment, pooled investigative site, BMI category ( $<30\text{kg/m}^2$ ,  $\geq 30\text{kg/m}^2$ ), and baseline migraine frequency ( $<8$  migraine headache days,  $\geq 8$  migraine headache days), as well as the continuous baseline CTT (hours).

The primary endpoint of this study for galcanezumab 240 mg and erenumab 140 mg will be estimated as the least squares (LS) mean change from baseline to Week 2 from the ANCOVA model. The type I error rate for the study will be controlled at a 2-sided 0.05 level.

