One possible explanation for the differences between reported frequencies of constipation in Phase 2 and 3 clinical trials, postmarketing clinician observation, and postmarketing AE reporting for monoclonal antibodies that act at the CGRP ligand versus the CGRP receptor could involve the effects of CGRP at the AMY1 receptor (Hay et al. 2018; Stauffer et al. 2018b; Aimovig package insert, 2020; Ashina et al. 2019; Hargreaves and Olesen 2019; Robbins 2019; Silberstein et al. 2019). By blocking the CGRP receptor, the CGRP receptor antagonist (erenumab) would decrease the motility-enhancing characteristics of CGRP while maintaining, or perhaps increasing, the GI motility-slowing effects via AMY1 receptor activation. Alternatively, the CGRP antagonist acting at the ligand would inhibit the motility-enhancing and motility-slowing effects of CGRP at the CGRP and AMY1 receptors, respectively, with the net effect being little to no change in GI transit time. This hypothesis will be studied in this clinical trial.

Abbreviations: AMY1 = amylin 1; CGRP = calcitonin gene-related peptide.

Figure CGBC.3.1. Mechanism of action of CGRP monoclonal antibodies.

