10.1. Sample Size Determination

Assuming within-group mean difference in CTT is about 4.2 hours with standard deviation of approximately 8, a sample of 30 patients in each treatment group will provide 80% power to detect the difference within the treatment group. The total sample size for the study would be 60.

Assuming 20% screen failure rate, approximately 75 patients may be screened to enroll 60 patients into the study. Eligible patients will be randomized in a 1:1 ratio to galcanezumab or erenumab to have about 30 patients in each treatment group.

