10.3.3. Efficacy Analyses

10.3.3.1. Primary Analyses

The primary objective is to assess changes in CTT between pre- and post-drug administration within each treatment group. The primary measure is the mean change from baseline in the CTT 2 weeks after drug administration within each treatment group.

The primary analysis will be performed using an analysis of covariance (ANCOVA) model. The analysis will include the categorical effects of treatment and all randomization stratification factors (site, baseline migraine frequency, and BMI category; see Section 7.2), as well as the continuous baseline CTT. Least squares mean change from baseline in each treatment group will be tested to detect any change in CTT between pre- and post-drug administration.

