Appendix 2.4. Publication Policy

The publication policy for Study I5Q-MC-CGBC is described in the Clinical Trial Agreement.

**Appendix 3. Protocol Amendment
I5Q-MC-CGBC(a) Summary
A Phase 4 Single-Blind Study of Gastrointestinal Transit
Time in Adult Patients with Migraine Before and After
Initiation of a mAb CGRP Antagonist**

Overview

Protocol I5Q-MC-CGBC(a) A Phase 4 Single-Blind Study of Gastrointestinal Transit Time in Adult Patients with Migraine Before and After Initiation of a mAb CGRP Antagonist has been amended. The new protocol is indicated by amendment (a) and will be used to conduct the study in place of any preceding version of the protocol.

The overall changes and rationale for the changes made to this protocol are described in the following table:

Amendment Summary for Protocol I5Q-MC-CGBC Amendment (a)

Section # and Name	Description of Change	Brief Rationale
Global	The study has been amended from an open-label study to a single-blind study.	This change was made to reduce potential for patient bias, as the frequency and consequences of constipation for erenumab and galcanezumab are not the same based on a recent USPI update for erenumab regarding constipation.
	Minor editorial changes	Minor editorial changes were made to improve clarity.
Title	CGRP Antagonist has been clarified to mAb CGRP Antagonist.	This clarification was made due to the recent approval of oral CGRP antagonists.
Section 2 Schedule of Activities	Vital sign assessments have been added to Visits 3, 4, and 5.	The additional vital sign assessments were added due to the April 2020 update to the erenumab USPI with Warning and Precautions language for new-onset or worsening of pre-existing hypertension based on postmarketing information.
Section 6.1 Inclusion Criteria	Chronic migraine has been removed from Inclusion Criterion [2].	The chronic migraine diagnosis was removed because this patient population has a higher frequency of headaches per month, which can be associated with more comorbidity. Therefore, this change was made to reduce variation in the population due to the small sample size and the exploratory nature of the study. Chronic migraine was also removed from Inclusion Criterion [4] due to this change.

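### SAP 6.10.1 claims study-wise control of type I error at 0.05, but the plan runs two primary tests at 0.05 each with no multiplicity procedure

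*SAP*

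**What the plan says.** SAP 6.10.1, on the primary analysis, ends with: "The type I error rate for the study will be controlled at a 2-sided 0.05 level".

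The rest of the plan works arm by arm:

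- **Endpoint.** SAP 4.1 defines it as the "change from baseline in CTT after administration of galcanezumab or erenumab within each treatment group in hours".
- **Test.** Protocol 10.3.3.1: "Least squares mean change from baseline in each treatment group will be tested to detect any change in CTT between pre- and post-drug administration".
- **Level.** SAP 6.1: "All tests of within-group and between-group comparisons will be conducted at a 2-sided alpha level of 0.05, unless otherwise stated". The same sentence stands in Protocol 10.3.1 and is the entire content of SAP 6.5, the multiplicity section.
- **Sample size.** Protocol 10.1 says that "a sample of 30 patients in each treatment group will provide 80% power to detect the difference within the treatment group", and SAP 5.2 agrees.

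Neither document splits alpha, orders the two tests, or requires both arms to be significant. The conditional step in SAP 6.10.4 only triggers an exploratory analysis of pressure parameters and does not protect the primary error rate.

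**The concern.** Read literally, the sentence in SAP 6.10.1 promises at most a 5% chance of any false primary finding across the two drugs. Two separate tests at 0.05 do not deliver that. The sentence could be carried into the study report, where a significant CTT change in one arm would appear to have study-wise protection that was never built in. What is at stake is the strength of the primary claim, not how the tests are run.

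**Working it through.** **1. Number of tests and level.** There are two primary tests, one per arm (Protocol 10.3.3.1), each at 2-sided 0.05 (SAP 6.1 and 6.5, Protocol 10.3.1).

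**2. Reproduce the stated power.** The inputs from Protocol 10.1 and SAP 5.2 are a change of 4.2 h, SD 8 and 30 patients per arm. SD 8 is taken as the SD of the within-patient change, which the documents do not say outright. For a one-sample t-test on the change, df = 29 and the noncentrality is (4.2/8) × √30 = 2.88.

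| Level per arm | Power, t-test | Power, normal approximation |
|---|---|---|
| 0.05 | 79.4% | 82.0% |
| 0.025 | 69.5% | 73.7% |

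The stated 80% is reproduced at an unadjusted 0.05 in each arm and not at 0.025. No adjustment was built into the sample size.

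**3. Nominal familywise rate.** The two arms contain different patients, so the tests are close to independent.

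- Neither drug changes CTT: 1 − (1 − 0.05)² = 0.0975, with an upper bound of 0.05 + 0.05 = 0.10 whatever the dependence. A correlation of 0.3 between the two test statistics gives 0.095.
- Only one arm is null: 0.05, because only one false finding is possible.

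These figures require each test to have an exact size of 0.05.

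**4. The planned ANCOVA.** The tests were simulated with neither drug having an effect. There were 40,000 trials per setting, 30 patients per arm and SD of change 8. The model held treatment, pooled site, BMI category, migraine-frequency category and baseline CTT. LS means were taken at equal factor weights and mean baseline. The following inputs are assumptions, not taken from the documents: 35% with BMI ≥30, 50% with ≥8 migraine headache days, and baseline/post-dose correlations of 0.3 to 0.8. The number of pooled sites was set at 3, 5 or 7; 7 is the most that the pooling rule of 4 per arm allows, since 30/4 = 7.5.

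| Baseline/post correlation | Familywise rate at 0.05 per arm |
|---|---|
| 0.8 | 10.7 to 10.8% |
| 0.7 | 11.1 to 11.5% |
| 0.5 | 12.6 to 12.8% |
| 0.3 | 14.3 to 14.8% |

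Per-arm size was 5.5 to 7.9%. In a second run (4 sites, 20,000 trials per setting), paired t-tests gave 9.2 to 10.0% familywise, against 10.8 to 14.6% for the ANCOVA. The LS-mean test treats the sample's mean baseline as fixed. When change depends on baseline, its standard error is then too small for the unconditional mean change. A simulation in which change did not depend on baseline (3 sites) gave 9.8%.

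**5. Effect of an adjustment.** At 0.025 per arm (Bonferroni; Holm is identical when neither drug has an effect), two tests of exact size give 1 − 0.975² = 4.94%. The 40,000-trial ANCOVA simulations gave 5.5 to 8.5% familywise and 2.8 to 4.4% per arm.

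**The case against.** The strongest reply is that the sentence is loose wording for the significance level. It follows an endpoint stated separately for each drug, and every operative part of the plan is per arm, so an analyst would run the same tests whatever the sentence says. Protocol Appendix 3 describes a restriction of eligibility as made "due to the small sample size and the exploratory nature of the study", and per-arm testing suits such a study. That stands: the tests need no change. The loose reading is the weaker one, however. The per-test level is already given elsewhere, and this sentence places the control at the level of the study. If only the per-test level was meant, the rewording says so.

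A second reply is that nearly 10% needs both drugs to be null, whereas Protocol 3.2 expects slowing with erenumab and, for an antibody acting on the ligand such as galcanezumab, inhibition of both effects "with the net effect being little to no change in GI transit time". Under that hypothesis the nominal rate is 5%. This is correct, but study-wise control must also cover the case in which neither drug acts.

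A third reply is that the excess of 10.7 to 14.8% over 9.75% is not multiplicity. That also stands. It is inflated per-arm size, it would arise with a single arm, and it depends on the assumed correlation. It shows only that 9.75% should not be presented as the actual rate or as a ceiling.

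**Conclusion.** The point holds. The plan claims study-wise control at 0.05 and provides a nominal 0.05 per arm. With exact-size, near-independent tests, the chance of at least one false primary finding is 9.75% if neither drug changes CTT and 5% if one arm is null. For the planned ANCOVA the first figure was 10.7 to 14.8% in simulation. That range rests on the assumed correlations, covariate splits and site numbers, and falls to about 9.8% if change does not depend on baseline. The defect is confined to one sentence. The choice to test each arm at 0.05 is defensible, and the stated sample size is consistent with it.

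**What to change.** In SAP 6.10.1, replace the sentence with: *Each within-group primary test uses a nominal 2-sided 0.05 level; the two tests are interpreted separately and the familywise type I error rate is not controlled.* Add the same statement to SAP 6.5. Do not print 9.75% as the study's error rate. The cost is one sentence replaced, one added, and the study-wise claim given up. Tests, patients and stated per-arm power stay as they are.

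If the sponsor prefers study-wise control, SAP 6.5 must name a procedure, and Protocol 10.1 and SAP 5.2 must restate the power. On the plan's sizing inputs (one-sample t-test, not the ANCOVA), power to detect 4.2 h in an arm is as follows. The 6 h effect is illustrative and not from the documents.

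| Procedure | Other arm 4.2 h | Other arm no effect | Other arm 6 h |
|---|---|---|---|
| Unadjusted 0.05 | 79.4% | 79.4% | 79.4% |
| Bonferroni, 0.025 each | 69.5% | 69.5% | 69.5% |
| Holm | 76.3% | 69.7% | 78.9% |
| Fixed sequence, arm tested second | 63.0% | 4.0% | 77.6% |

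Holm is 0.6945 + (0.7937 − 0.6945) × q, where q is the other arm's power at 0.025 (0.6945, 0.025 or 0.954). The fixed sequence is 0.7937 times the first arm's power at 0.05 (0.7937, 0.05 or 0.978). With Bonferroni, 80% power needs about 38 patients per arm by the t-test (35 by the normal approximation) against the planned 30. Control by any of these would still be nominal while the primary tests are ANCOVA LS-mean tests, as step 5 of the working shows for Bonferroni and Holm.
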